Summary statistics (n, mean, median, SD, minimum, and maximum) will be computed on the raw and change from baseline values for standard vital sign measurements (temperature and respiratory rate) by visit and time for each treatment. The Day 1 prior to treatment time point will serve as baseline. If there are multiple vital signs taken at any time point, then the latest set of vital signs

will be used for the analysis.

Additionally, summary statistics will be computed on the raw and change from baseline values for the orthostatic vital sign measurements (BP and HR) by visit and time for each treatment. The Day 1 prior to treatment time point will serve as baseline. Spaghetti plots of the raw values for orthostatic diastolic BP, orthostatic systolic BP and orthostatic HR will be displayed by patient, time point and treatment.

All vital signs will be provided in data listings as shown in Appendix B. Vital signs taken while standing will be included in the data listings but will not be summarized in the tables.

Physical Examination

All physical examination results will be listed as shown in Appendix B.

ECG

The ECG parameters of interest include HR, PQ, QRS, QT, RR, and QTcF along with information on T and U waves.

As the ECGs are performed in triplicate at Day 1 prior to treatment, the average of the three values for each of the ECG parameters will be used as the baseline value. Summary statistics (n, mean, median, SD, minimum, and maximum) will be computed on the raw and change from baseline values for each parameter by visit and time by treatment and overall. The Day 1 prior to treatment time point will serve as baseline. Spaghetti plots of the raw values for HR and QTcF will be displayed by patient, time point and treatment.

The ECG Interpretations for each of the three ECGs on Day 1 prior to treatment will be used to obtain a Combined Overall ECG Interpretation. The Combined Overall ECG Interpretation in relation to clinical significance at Day 1 prior to treatment (i.e., baseline) will be determined as follows:

- If at least one ECG Interpretation = 'Abnormal – clinically significant', then the Combined Overall ECG Interpretation = 'Abnormal – clinically significant'.
- Else if there are no readings such that ECG Interpretation = 'Abnormal – clinically significant' and there is at least one ECG Interpretation = 'Abnormal – not clinically significant', then the Combined Overall ECG Interpretation = 'Abnormal – not clinically significant'.

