8.0 List of Analysis Tables, Figures and Listings

Table No.	Table Title	Included in Final Tables	Shown in Appendix B
1	Patient Disposition	X	X
2	Demographics and Baseline Data Summary Statistics—Continuous Variables (Safety Population)	X	X
3	Demographics and Baseline Data Summary Statistics—Categorical Variables (Safety Population)	X	X
4	Summary of Adverse Events (Safety Population)	X	X
5	Number and Proportion of Patients with Adverse Events (Safety Population)	X	X
6	Number and Proportion of Patients with Treatment-Related Adverse Events (Safety Population)	X	X
7	Number and Proportion of Patients with Treatment-Related Adverse Events that Led to Study Drug Discontinuation (Safety Population)	X	X
8	Number and Proportion of Patients with Serious Adverse Events (Safety Population)	X	X
9	Number and Proportion of Patients with Treatment-Related Serious Adverse Events (Safety Population)	X	X
10	Number and Proportion of Patients with Treatment-Related Serious Adverse Events that Led to Study Drug Discontinuation (Safety Population)	X	X
11	Number and Proportion of Patients with Adverse Events of Special Interest (Safety Population)	X	X
12	Number and Proportion of Patients with Adverse Events of Special Interest that Led to Study Drug Discontinuation (Safety Population)	X	X
13	Number and Proportion of Patients with Adverse Events by Relationship to Study Drug (Safety Population)	X	X
14	Number and Proportion of Patients with Adverse Events by Severity (Safety Population)	X	X
15	Vital Sign Parameter Summary Statistics (Safety Population)	X	X
16	Orthostatic Vital Sign Parameter Summary Statistics (Safety Population)	X	X
17	ECG Parameter Summary Statistics (Safety Population)	X	X
18	ECG Results Shift Table by Visit and Clinical Significance (Safety Population)	X	X
19	ECG Results Shift Table by Visit (Safety Population)	X	X
20	Blood Chemistry Parameter Summary Statistics (Safety Population)	X	X
21	Hematology Parameter Summary Statistics (Safety Population)	X	
22	Coagulation Parameter Summary Statistics (Safety Population)	X	
23	Quantitative Urinalysis Parameter Summary Statistics (Safety Population)	X	
24	Summary of Qualitative Urinalysis Results by Parameter (Safety Population)	X	X

Table No.	Table Title	Included in Final Tables	Shown in Appendix B
25	Blood Chemistry Results Shift Table by Visit and Clinical Significance (Safety Population)	X	X
26	Hematology Results Shift Table by Visit and Clinical Significance (Safety Population)	X	

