27	Coagulation Results Shift Table by Visit and Clinical Significance (Safety Population)	X	
28	Quantitative Urinalysis Results Shift Table by Visit and Clinical Significance (Safety Population)	X	
29	Blood Chemistry Results for Electrolytes Shift Table by Visit and Clinical Significance (Safety Population)	X	
30	Blood Chemistry Results for Electrolytes Shift Table by Visit and Range of Normal Results (Safety Population)	X	X
31	Number and Proportion of Patients with Blood Chemistry Results for Electrolytes Outside of Normal Range (Safety Population)	X	X
32	Summary Statistics of Ibudilast and Bumetanide Plasma Concentration Levels by Treatment, Visit and Time (PK Population)	X	X
33	Summary Statistics of Ibudilast and Bumetanide Urine Concentration Levels by Treatment, Visit and Time (PK Population)	X	X
34	Summary Statistics of Estimated PK Plasma Parameters for Ibudilast by Treatment (PK Population)	X	X
35	Summary Statistics of Estimated PK Plasma Parameters for Bumetanide by Treatment (PK Population)	X	X
36	Summary Statistics of Estimated PK Urine Parameters for Ibudilast by Treatment (PK Population)	X	X
37	Summary Statistics of Estimated PK Urine Parameters for Bumetanide by Treatment (PK Population)	X	
38		X	X
39	KitAP Summary Statistics (Exploratory Population)	X	
40	OACIS-C Summary Statistics (Exploratory Population)	X	X
41	Summary of Responses for OACIS-C Assessment by Question (Exploratory Population)	X	X
42	Summary of Responses for OACIS-S Assessment by Question (Exploratory Population)	X	X
43	ABC-C Summary Statistics (Exploratory Population)	X	X
44	SRS-2 Summary Statistics (Exploratory Population)		
45	Summary of Responses for CSHQ Assessment by Question (Exploratory Population)	X	X
46	Lactate and Pyruvate Blood Level Summary Statistics (Exploratory Population)	X	X
47	Summary of Responses for CGI-S Assessment by Visit (Exploratory Population)	X	X
48	Summary of Responses for CGI-I Assessment by Visit (Exploratory Population)	X	X
49	Number and Proportion of Patients with Medical History Events (Safety Population)	X	X

Table No.	Table Title	Included in Final Tables	Shown in Appendix B
50	Number and Proportion of Patients Taking Concomitant Medications by ATC Level 4 and Preferred Term (Safety Population)	X	X

Listing No.	Listing Title	Included in Final Listings	Shown in Appendix B
DL1	Patient Disposition Data Listing	X	X
DL2	Demographics Data Listing	X	X
DL3	Adverse Events Data Listing	X	X
DL4	Vital Signs Data Listing	X	X

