DL5	Baseline ECG Data Listing	X	X
DL6	ECG Data Listing	X	X
DL7	Blood Chemistry Laboratory Results Data Listing	X	X
DL8	Serology Laboratory Results Data Listing	X	X
DL9	Hematology Laboratory Results Data Listing	X	X
DL10	Coagulation Laboratory Results Data Listing	X	
DL11	Urinalysis Laboratory Results Data Listing	X	
DL12	Hearing Assessment Data Listing	X	X
DL13	Pharmacokinetic Blood Sample Data Listing	X	X
DL14	Pharmacokinetic Urine Sample Data Listing	X	X
DL15	Plasma Concentrations Data Listing	X	X
DL16	Urine Concentrations Data Listing	X	X
DL17	Plasma Pharmacokinetics Parameters Data Listing	X	X
DL18	Urine Pharmacokinetics Parameters Data Listing	X	X
DL19	C-SSRS Data Listing	X	X
DL20	C-CASA Data Listing	X	X
DL21	OACIS-S Data Listing	X	X
DL22	OACIS-C Data Listing	X	X
DL23	SRS-2 Data Listing	X	X
DL24	SB5 ABIQ Data Listing	X	X
DL25	[REDACTED]	X	X
DL26	KiTAP Data Listing	X	
DL27	ABC-C Data Listing	X	X
DL28	CSHQ Data Listing	X	X
DL29	Lactate-Pyruvate Data Listing	X	X
DL30	CGI-S/CGI-I Data Listing	X	X
DL31	Medical History Data Listing	X	X
DL32	Concomitant Medications Data Listing	X	X
DL33	Physical Exam Data Listing	X	X
DL34	Study Drug Administration Data Listing	X	X
DL35	Drug Accountability Data Listing	X	X
DL36	Urine Pregnancy Test Data Listing	X	X
DL37	Protocol Deviations Data Listing	X	X
DL38	Patients Excluded from Safety Population Data Listing	X	X
DL39	Patients Excluded from PK Population Data Listing	X	

Listing No.	Listing Title	Included in Final Listings	Shown in Appendix B
DL40	Patients Excluded from Exploratory Population Data Listing	X	

Figure No.	Figure Title	Included in Final Listings	Shown in Appendix B
FIG1	Orthostatic Vital Signs - Spaghetti Plot of Systolic Blood Pressure by Patient, Time and Treatment (Safety Population)	X	X
FIG2	Orthostatic Vital Signs - Spaghetti Plot of Diastolic Blood Pressure by Patient, Time and Treatment (Safety Population)	X	
FIG3	Orthostatic Vital Signs - Spaghetti Plot of Heart Rate by Patient, Time and Treatment (Safety Population)	X	
FIG4	ECG Parameters - Spaghetti Plot of Heart Rate by Patient, Time and Treatment (Safety Population)	X	
FIG5	ECG Parameters - Spaghetti Plot of QTcF by Patient, Time and Treatment (Safety Population)	X	
FIG6	Blood Chemistry - Spaghetti Plot of Sodium by Patient, Time and Treatment (Safety Population)	X	X
FIG7	Blood Chemistry - Spaghetti Plot of Chloride by Patient, Time and Treatment (Safety Population)	X	

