Patients with at Least One AE	xxx (xxx)	xxx (xxx)	xxx (xxx)	xxx (xxx)	xxx (xxx)	xxx (xxx)	xxx (xxx)	xxx (xxx)	xxx (xxx)	xxx (xxx)
System Organ Class 1	xxx (xxx)	xxx (xxx)	xxx (xxx)	xxx (xxx)	xxx (xxx)	xxx (xxx)	xxx (xxx)	xxx (xxx)	xxx (xxx)	xxx (xxx)
Preferred Term 1	xxx (xxx)	xxx (xxx)	xxx (xxx)	xxx (xxx)	xxx (xxx)	xxx (xxx)	xxx (xxx)	xxx (xxx)	xxx (xxx)	xxx (xxx)
Preferred Term 2	xxx (xxx)	xxx (xxx)	xxx (xxx)	xxx (xxx)	xxx (xxx)	xxx (xxx)	xxx (xxx)	xxx (xxx)	xxx (xxx)	xxx (xxx)
System Organ Class 2	xxx (xxx)	xxx (xxx)	xxx (xxx)	xxx (xxx)	xxx (xxx)	xxx (xxx)	xxx (xxx)	xxx (xxx)	xxx (xxx)	xxx (xxx)
Preferred Term 1	xxx (xxx)	xxx (xxx)	xxx (xxx)	xxx (xxx)	xxx (xxx)	xxx (xxx)	xxx (xxx)	xxx (xxx)	xxx (xxx)	xxx (xxx)
Preferred Term 2	xxx (xxx)	xxx (xxx)	xxx (xxx)	xxx (xxx)	xxx (xxx)	xxx (xxx)	xxx (xxx)	xxx (xxx)	xxx (xxx)	xxx (xxx)

^aAdverse events coded with MedDRA Coding Dictionary Version XXX.

^bThe denominator for all proportions is the number of Safety population patients in the corresponding treatment group.

STATKING Clinical Services (month, day, year)

Source Program: xxxxxxxx.sas

Page x of y

Statistical Analysis Plan

STP1-C004

Page x of y

Table 15. Vital Sign Parameter Summary Statistics
STALICIA SA – Study No. STP1-C004
Safety Population (N=xxxx)

Treatment (units) ^a	Parameter	Visit	Time	Data Type ^b	n	Mean	Std Dev	Median	Min	Max
STP1- X mg ibudilast (xxx)	xxxxxxxxxx	Baseline	xxxx	RAW	xxx	xxx	xxx	xxx	xxx	xxx
	xxxxxx		xxxx	RAW	xxx	xxx	xxx	xxx	xxx	xxx
			xxxx	CFB	xxx	xxx	xxx	xxx	xxx	xxx
	xxxxxx		xxx	RAW	xxx	xxx	xxx	xxx	xxx	xxx
			xxx	CFB	xxx	xxx	xxx	xxx	xxx	xxx
STP1- X mg ibudilast (xxx)	xxxxxxxxxx	Baseline	xxxx	RAW	xxx	xxx	xxx	xxx	xxx	xxx
	xxxxxx		xxxx	RAW	xxx	xxx	xxx	xxx	xxx	xxx
			xxxx	CFB	xxx	xxx	xxx	xxx	xxx	xxx
Placebo (xxx)	xxxxxxxxxx	Baseline	xxxx	RAW	xxx	xxx	xxx	xxx	xxx	xxx
	xxxxxx		xxx	RAW	xxx	xxx	xxx	xxx	xxx	xxx
			xxx	CFB	xxx	xxx	xxx	xxx	xxx	xxx
Placebo (xxx)	xxxxxxxxxx	Baseline	xxxx	RAW	xxx	xxx	xxx	xxx	xxx	xxx
	xxxxxx		xxx	RAW	xxx	xxx	xxx	xxx	xxx	xxx
			xxx	CFB	xxx	xxx	xxx	xxx	xxx	xxx
Placebo (xxx)	xxxxxxxxxx	Baseline	xxxx	RAW	xxx	xxx	xxx	xxx	xxx	xxx
	xxxxxx		xxx	RAW	xxx	xxx	xxx	xxx	xxx	xxx
			xxx	CFB	xxx	xxx	xxx	xxx	xxx	xxx

Vital sign parameters in this table include temperature and respiratory rate.

^b RAW = observed data recorded in database; CFB = change from baseline = (results at current visit) – (Baseline results).
STATKING Clinical Services (month, day, year)

Source Program: xxxxxxx.sas

a

Statistical Analysis Plan

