STP1-C004

Table 16. Orthostatic Vital Sign Parameter Summary Statistics
STALICLA SA – Study No. STP1-C004
Safety Population (N=xxxx)

Treatment	Parameter (units) ^a	Visit	Time	Data Type ^b	n	Mean	Std Dev	Median	Min	Max
STP1-████mg ibudilast (xxxx)	xxxxxxxxxx	Baseline	xxxx	RAW	xxx	xxx	xxx	xxx	xxx	xxx
	xxxxxx		xxxx	RAW	xxx	xxx	xxx	xxx	xxx	xxx
			xxxx	CFB	xxx	xxx	xxx	xxx	xxx	xxx
	xxxxxx									
	xxxxxx		xxxx	RAW	xxx	xxx	xxx	xxx	xxx	xxx
				CFB	xxx	xxx	xxx	xxx	xxx	xxx
STP1-████mg ibudilast (xxxx)	xxxxxxxxxx	Baseline	xxxx	RAW	xxx	xxx	xxx	xxx	xxx	xxx
	xxxxxx		xxxx	RAW	xxx	xxx	xxx	xxx	xxx	xxx
			xxxx	CFB	xxx	xxx	xxx	xxx	xxx	xxx
	xxxxxx									
Placebo	xxxxxxxxxx (xxxx)	Baseline	xxxx	RAW	xxx	xxx	xxx	xxx	xxx	xxx
	xxxxxx		xxxx	RAW	xxx	xxx	xxx	xxx	xxx	xxx
			xxxx	CFB	xxx	xxx	xxx	xxx	xxx	xxx
	xxxxxx									
	xxxxxx		xxxx	RAW	xxx	xxx	xxx	xxx	xxx	xxx
				CFB	xxx	xxx	xxx	xxx	xxx	xxx
	xxxxxx		xxxx	RAW	xxx	xxx	xxx	xxx	xxx	xxx
				CFB	xxx	xxx	xxx	xxx	xxx	xxx

Vital sign parameters in this table include orthostatic heart rate, orthostatic diastolic blood pressure, and orthostatic systolic blood pressure taken in the supine position.

^b RAW = observed data recorded in database; CFB = change from baseline = (results at current visit) – (Baseline results).

STATKING Clinical Services (month, day, year)

Source Program: xxxxxxx.sas

Page x of y

Statistical Analysis Plan

STP1-C004

Table 17. ECG Parameter Summary Statistics

STALICLA SA – Study No. STP1-C004
Safety Population (N=xxxx)

Page x of y

Treatment	Parameter (units)	Visit ^a	Time	Data Type ^b	n	Mean	Std Dev	Median	Min	Max
STP1- XX mg ibudilast	xxxxxxxxxx (xxxx)	Baseline	xxxx	RAW	xxx	xxx	xxx	xxx	xxx	xxx
	xxxxxxxxxx			RAW	xxx	xxx	xxx	xxx	xxx	xxx
				CFB	xxx	xxx	xxx	xxx	xxx	xxx
				RAW	xxx	xxx	xxx	xxx	xxx	xxx
				CFB	xxx	xxx	xxx	xxx	xxx	xxx
STP1- XX mg ibudilast	xxxxxxxxxx (xxxx)	Baseline	xxxx	RAW	xxx	xxx	xxx	xxx	xxx	xxx
	xxxxxxxxxx			RAW	xxx	xxx	xxx	xxx	xxx	xxx
				CFB	xxx	xxx	xxx	xxx	xxx	xxx
Placebo	xxxxxxxxxx (xxxx)	Baseline	xxxx	RAW	xxx	xxx	xxx	xxx	xxx	xxx
	xxxxxxxxxx			RAW	xxx	xxx	xxx	xxx	xxx	xxx
				CFB	xxx	xxx	xxx	xxx	xxx	xxx
Overall	xxxxxxxxxx (xxxx)	Baseline	xxxx	RAW	xxx	xxx	xxx	xxx	xxx	xxx
	xxxxxxxxxx			RAW	xxx	xxx	xxx	xxx	xxx	xxx
				CFB	xxx	xxx	xxx	xxx	xxx	xxx

The baseline raw value for each parameter is calculated using the average of the triplicate values from the ECG performed on Day 1 pre-dose.

^b Raw = observed data; CFB = change from baseline = (results at current visit) - (Baseline results).

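### SAP Table 16 carries the orthostatic title but holds supine values only, and no table reports standing BP or HR or the standing-minus-supine difference

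*SAP*

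**What the plan says.** **Protocol.** The synopsis (primary safety endpoints) and section 3.3.1 list change from baseline in SBP, DBP, heart rate and respiratory rate on one line, and change from baseline in orthostatic BP and heart rate on another. Section 4.6.1.3 gives the procedure: a supine reading after about 5 minutes of rest, then standing readings at 1 and 3 minutes. Section 5.1.3 makes orthostasis an adverse event of special interest (AESI), defined by a fall on standing. Section 6.4 plans, as appropriate, a summary of the incidence of BP abnormalities.

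**SAP section 4.2.** It first promises that "summary statistics will be computed on the raw and change from baseline values for the orthostatic vital sign measurements (BP and HR") by visit, time and treatment. It then says: "Vital signs taken while standing will be included in the data listings but will not be summarized in the tables".

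**SAP section 8.0 and Appendix B.** Table 16 is titled "Orthostatic Vital Sign Parameter Summary Statistics (Safety Population"). Its footnote reads: "Vital sign parameters in this table include orthostatic heart rate, orthostatic diastolic blood pressure, and orthostatic systolic blood pressure taken in the supine position". Change is defined there as current visit minus baseline. The only other vital-sign table is Table 15, whose footnote reads: "Vital sign parameters in this table include temperature and respiratory rate". Standing readings appear in Data Listing 4, identified by patient position. That shell has no column for the difference.

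**The concern.** A postural measurement is a comparison of two positions. A table restricted to one position cannot show it, whatever its title. Because Table 15 leaves out BP and heart rate, Table 16 is really the resting BP and heart-rate table, and the separate orthostatic endpoint has no tabular summary.

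This matters for this product. Protocol section 1.5.2 says the loop diuretic component may trigger hypokalemia and hypotension, and commits to monitoring electrolytes and orthostatic BP at each post-dose visit. Electrolytes receive three dedicated tables (29, 30 and 31), the last being "Number and Proportion of Patients with Blood Chemistry Results for Electrolytes Outside of Normal Range (Safety Population"). Standing BP and heart rate receive none. A flat Table 16 could be read as showing no postural effect by anyone who misses the footnote.

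**Working it through.** The plan gives no figure to reproduce. The check is a comparison of passages, followed by arithmetic on what the tables would and would not show.

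**1. Does any table carry the quantity?** Of the 50 tables in SAP section 8.0, two cover vital signs: 15 (temperature and respiratory rate) and 16 (supine BP and heart rate). The phrase about the supine position in the Table 16 footnote could be read as attaching only to systolic BP. The section 4.2 sentence bars every standing vital sign from the tables, so that reading makes no difference. Number of tables with a standing value or a standing-minus-supine difference: 0.

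**2. How much measured data is left out of the tables?** Each set has 3 readings (supine, 1 minute, 3 minutes) of 3 parameters (SBP, DBP, HR).

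- Per set: 3 × 3 = 9 values, of which 2 × 3 = 6 are standing.
- Protocol Appendix 1 gives 6 sets from Day 1 to Day 28 (Day 1 pre- and post-dose, Day 7, Day 14 pre- and post-dose, Day 28): 36 of 54 values per patient are standing.
- SAP section 1.2 marks Day 1 as pre- and post-dose but not Day 14, giving 5 sets: 30 of 45.
- 36/54 = 30/45 = 0.667.
- Six active patients with complete data: 216 of 324, or 180 of 270.

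**3. What could Table 16 miss?** These are constructed examples, not predictions. Each assumes six active patients, no symptoms and perfect site reporting. The postural change is (standing − supine on Day 14) − (standing − supine at baseline).

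| Example | Supine, both visits | Standing, baseline | Standing, Day 14 | Table 16 change | Postural change |
|---|---|---|---|---|---|
| A: SBP, all six | 120 | 118 | 101 | 120 − 120 = 0 | (101 − 120) − (118 − 120) = −17 |
| B: HR, all six | 70 | 76 | 106 | 70 − 70 = 0 | (106 − 70) − (76 − 70) = +30 |
| C: SBP, one of six | 120 | 118 | 95 | mean 0, minimum 0 | (95 − 120) − (118 − 120) = −23; mean −23/6 = −3.8 |

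- **A.** The Day 14 fall is 19 mm Hg. It is neither over 20 (section 5.1.3) nor 20 or more (section 4.6.1.3), so the AESI tables show 0 of 6.
- **B.** The AESI definition has no heart-rate term, so nothing is counted.
- **C.** The fall of 25 mm Hg is an AESI. If reported, Tables 4 and 11 show 1/6 = 16.7%, with no visit and no size.

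**4. Do other outputs fill the gap?** AESIs are counted by treatment in Tables 4, 11 and 12; Table 11 is "Number and Proportion of Patients with Adverse Events of Special Interest (Safety Population"). Those counts rest on site reporting and give no magnitude. Protocol section 5.3.5.5 says not every vital-sign abnormality is an adverse event, so an asymptomatic fall might go unreported despite section 5.1.3. Figures 1 to 3, such as "Orthostatic Vital Signs - Spaghetti Plot of Systolic Blood Pressure by Patient, Time and Treatment (Safety Population"), plot raw values. The SAP text does not say in which position, and the figure shells are not visible in the public copy.

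**5. A related inconsistency.** Protocol section 4.6.1.3 calls a drop of 20 or more systolic, or 10 or more diastolic, abnormal. Sections 3.1.2 and 5.1.3 use falls over 20 or over 10. A fall of exactly 20 or 10 meets the section 4.6.1.3 criterion but not the one in sections 3.1.2 and 5.1.3.

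**The case against.** The best defence is that the protocol leaves vital-sign tables to discretion. Section 6.4.3 specifies individual listings and adds tabular summaries as appropriate. Listing 4 shows every standing value, and the SAP discloses the supine restriction in both the text and the footnote. The protocol never defines the derived orthostatic variable, so standing minus supine is an inference. Figures 1 to 3 may plot standing readings. The DSMB's review before escalation includes orthostatic BP changes (section 3.1.3), and symptoms on standing are recorded as adverse events. With possibly 3 patients at the highest dose (SAP section 1.1), means are fragile and individual display is reasonable. The examples are built to make the point, and the two-thirds figure merely reflects two standing readings per supine one.

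Much of this is fair as context. No data are lost, and the escalation decision does not rest on Table 16. The examples say nothing about how likely such data are.

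It does not rescue the plan. The SAP itself undertakes to summarise the orthostatic measurements, and section 2.1 promises descriptive statistics for all variables. That overtakes the protocol's discretion. A listing is not a summary by treatment, and raw plots with no stated position are not a summary of postural change. Small numbers apply equally to the vital-sign, ECG and laboratory variables the SAP does tabulate. The separate endpoint line and the supine-then-standing procedure leave little room for orthostatic to mean supine.

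**Conclusion.** The concern holds. This is a stated rule that yields the wrong quantity for a primary safety endpoint: resting change appears under an orthostatic title, and none of the 50 tables shows standing values or postural change. Six of every nine values in each set are excluded from the tables. A uniform 17 mm Hg worsening in the systolic postural fall, or a 30 beats-per-minute increase in the postural heart-rate rise, could leave Table 16 at zero and the AESI counts at nought.

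The conclusion rests on reading orthostatic as a comparison of standing with supine, which the protocol's procedure and AESI definition support without formally defining the derived variable. The counts assume complete data, and the examples show what is possible, not what is expected. Whether Figures 1 to 3 include standing readings cannot be settled from the text.

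**What to change.** In SAP section 4.2 and Appendix B:

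- Delete the clause that keeps standing readings out of the tables.
- Retitle Table 16 and its footnote as supine (resting) BP and heart rate.
- Add a table of standing SBP, DBP and HR, and of the standing-minus-supine differences, at 1 and 3 minutes. Show raw values and change from Day 1 pre-dose, by visit, time and treatment.
- Add the number and proportion of patients with a measured orthostatic fall, by visit and at any post-dose time, by treatment. Program this after the sponsor has reconciled the threshold wording in protocol section 4.6.1.3 with that in sections 3.1.2 and 5.1.3, or has stated that both are to be counted.
- State which position Figures 1 to 3 plot.

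A secondary point: the out-of-range flagging that protocol section 6.4.3 requires in the vital-signs listing needs a vital-sign normal range from the sponsor. The documents give none.

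The cost is SAP text, table shells and modest programming, since all readings are already collected. The SAP is a signed version 1.1, and its Appendix A says format changes after approval carry programming charges. Only the fall count has to wait for a sponsor statement.
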